In addition to observations related to the shadowing of clinicians, we will conduct observations and informal conversations with clinical staff in clinical and staff-only areas of the hospitals, as needed. This data collection may be conducted outside the times when we are shadowing the clinicians. This additional time for observations and informal conversations will provide contextual data on how ReSPECT is used, including descriptions of the ward environments where clinicians engage with the ReSPECT form and where they discuss the ReSPECT process and form with one another. As part of these observations, we may take photographs involving the ReSPECT form; these photographs will document, for example, where the form is stored, advertised, and placed within the wider structure of the ward. All photographs will be of the Respect form, posters, and surrounding material objects. We will not take any photographs of patient data or of people. In addition, the researcher will initiate and / or participate in informal conversations with clinical staff members such as nurses, junior doctors, and consultants. The researcher will obtain verbal consent from the participating staff members to write up these conversations, or any part thereof (in quoted or paraphrased form), as field notes, to be used in data analysis. All field notes will anonymise participants and exclude or alter identifying information; pseudonyms will be used throughout, and the clinical staff members' names will not be recorded.

Sampling for interviews: We take a stratified sample of cases for interviews according to the ReSPECT treatment choices. We will oversample for cases where the patient has been observed to bring to the hospital a ReSPECT completed outside of the hospital or other similar document (e.g. DNACPR form). These cases will enable us to explore the community-hospital interface relevant to the ReSPECT form. We will sample for interviews until data saturation is

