5.1.1 Aim

The overall aim of this work package is to explore how widely ReSPECT is being used amongst

patients in hospital and to examine associations between recommendations and patient

ReSPECT Evaluation Protocol Version 5.0, dated 20.06.19, IRAS project ID: 204688 characteristics and their outcomes.

Within this broad framework, we will explore if DNACPR recommendations which are made in the context of an overall ReSPECT increase the risk of certain harms when compared with not having a DNACPR order in place.

This work package will also provide a broad understanding about how the ReSPECT process is used in practice.

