5.3 Data Collection for WP3

The following information will be extracted from the clinical and audit/or records:

(1) Demographics (age, gender, ethnicity, abbreviate home postcode as a proxy for social class), (2) Reason for admission, (3) Co-morbidities: Cognitive impairment (dementia, learning difficulties), Charlson co-morbidity index [56], GO-FAR sore [57] (both of which predict outcome from cardiac arrest), assessment of whether their condition is likely to be fatal (measured by McCabe Scale [58]), (4) ReSPECT (patient preference, emergency care treatment decisions, resuscitation status, capacity, who was involved in the discussions, when, where and by whom was the decision made), (5) NHS Safety Thermometer Audit data, (6) Length of hospital stay, survival to discharge, discharge location.

We will endeavour to ensure that researchers collect baseline data blind to ReSPECT classification. Practically what this means is that the researcher will first extract the baseline data, some of which may need some interpretation. Only when this is complete will they extract ReSPECT classification data which does not require any interpretation.

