Nevertheless, for generalisability we need to ensure a reasonable spread of patients/decisions, and in order to model risk of harm we need sufficient harmful events to have occurred. Based on our pilot data we expect 70% of patients to have a ReSPECT decision, of whom 20% will have a DNACPR decision. 20-30% will have no decision, which by default means they would receive resuscitation in the event of cardiac arrest. We therefore intend to enrol 3000 patients in this study (minimum 500 patients per site, six sites). Assuming a "harm rate" of 6.5% (based on 2014 NHS Thermometer data), this will provide 200 incidences of harm for the risk modelling. If possible, for the modelling of harms, we will match cases to controls in order to increase statistical power.

6. WORK PACKAGE 4 - FOCUS GROUPS WITH GENERAL PRACTITIONERS, COLLECTION OF CONTEXTUAL DATA ON IMPLEMENTATION AT SITES, SYNTHESIS OF FINDINGS AND IDENTIFICATION OF AREAS FOR IMPROVEMENT AND FURTHER WORK

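### WP3 takes resuscitation status from the ReSPECT form, so patients with a DNACPR order on another form may sit in the no-DNACPR comparator

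*Protocol*

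**What the plan says.** The aim of WP3 (Protocol 5.1.1) is to see whether DNACPR recommendations made within ReSPECT "increase the risk of certain harms when compared with not having a DNACPR order in place". The comparator is therefore patients with no DNACPR order of any kind.

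The data to support this are set out in 5.3. Resuscitation status is a component of the fourth item, "ReSPECT (patient preference, emergency care treatment decisions, resuscitation status, capacity, who was involved in the discussions". No item covers a DNACPR order on another document. Section 5.1.4 says that, for patients without a ReSPECT decision, its absence will be extracted. Section 5.5 treats resuscitation status as two-valued, DNACPR or for resuscitation.

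The sample-size paragraph of 5.5 gives the expected split: "we expect 70% of patients to have a ReSPECT decision, of whom 20% will have a DNACPR decision". It then adds: "20-30% will have no decision, which by default means they would receive resuscitation in the event of cardiac arrest".

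Elsewhere the protocol expects other forms. WP1a question 2 (3.2.1) asks what happens when a patient brings in a ReSPECT or similar document. The interview sampling in 3.2.4 oversamples patients who bring "a ReSPECT completed outside of the hospital or other similar document (e.g. DNACPR form". WP1 and WP3 use the same six hospitals.

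**The concern.** A patient with a valid community DNACPR form and no ReSPECT form has a DNACPR order in place. Under the data listed in 5.3, that patient can be recorded only as lacking a ReSPECT decision, and under the default in 5.5 would count as for resuscitation. This is the opposite of the patient's true status on the exposure that WP3 studies.

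Three results are exposed:

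- **The harm contrast (question 5).** If these patients share any excess harm linked to DNACPR orders, the comparator's harm rate rises and the odds ratio moves toward 1. Section 5.3.1 treats more harm under DNACPR as a signal that further work is needed, so the error leans toward reassurance.
- **The models of who receives a DNACPR (questions 3 and 4).** Holders of other forms become false negatives in the outcome wherever they are included.
- **The No Decision level of the care-group model.** It would mix patients with no decision and patients whose decision is recorded elsewhere.

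An analysis plan can choose a coding rule, but it cannot recover a variable that was not collected.

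**Working it through.** **Inputs from Protocol 5.5:** 3000 patients ("We therefore intend to enrol 3000 patients in this study (minimum 500 patients per site, six sites"); 70% with a ReSPECT decision; 20% of those with a DNACPR; 20-30% with no decision; harm rate 6.5%.

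**Step 1. The plan's own figure, and who must be in it.**
- 3000 × 0.065 = 195, which reproduces the stated 200 after rounding.
- Patients with a ReSPECT decision only: 3000 × 0.70 = 2100, and 2100 × 0.065 = 136.5.
- So the 200 harms need the patients without a form to be in the risk modelling.

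**Step 2. Group sizes.**
- ReSPECT DNACPR: 3000 × 0.70 × 0.20 = 420.
- Everyone else under two-valued coding: 3000 − 420 = 2580.
- No decision: 3000 × 0.20 = 600 to 3000 × 0.30 = 900.

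**Step 3. Misclassified patients.** The protocol gives no share of no-decision patients holding another DNACPR form. I assume 5%, 10% and 20%. With k such patients, the share of the comparator is k/2580 and the share of all DNACPR holders is k/(420 + k).

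| Assumed share | k (of 600 to 900) | k/2580 | k/(420 + k) |
|---|---|---|---|
| 5% | 30 to 45 | 1.2% to 1.7% | 6.7% to 9.7% |
| 10% | 60 to 90 | 2.3% to 3.5% | 12.5% to 17.6% |
| 20% | 120 to 180 | 4.7% to 7.0% | 22.2% to 30.0% |

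**Step 4. Effect on the crude harm odds ratio.** Take 6.5% as the risk in true non-holders (odds 0.065/0.935 = 0.0695). A true odds ratio of 1.5 gives DNACPR odds 0.1043, risk 0.0944. The contaminated comparator risk is 0.065 + (k/2580) × (risk in hidden holders − 0.065).

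- k = 30, hidden holders at the DNACPR risk: 0.0653, odds 0.0699, observed odds ratio 0.1043/0.0699 = 1.49.
- k = 180, same risk: 0.0671, odds 0.0719, observed odds ratio 1.45.
- If hidden holders are at higher risk (assumed odds ratio 3, risk 0.1726), k = 30 gives 1.47 and k = 180 gives 1.33.
- The most extreme case tried, 30% of 900 (k = 270) with hidden holders at odds ratio 3, gives 1.26.

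**Step 5. Cost of restricting to patients with a ReSPECT form.** The comparator becomes 3000 × 0.70 × 0.80 = 1680. At 6.5% harm in both groups, the variance of the log odds ratio is 1/(n₁ × 0.065 × 0.935) + 1/(n₀ × 0.065 × 0.935).

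- 420 against 2580: 0.0392 + 0.0064 = 0.0456, standard error 0.213.
- 420 against 1680: 0.0392 + 0.0098 = 0.0490, standard error 0.221.

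The standard error rises by about 4%, because the 420 DNACPR patients dominate the variance.

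**The case against.** The strongest reply is that no coding rule is written. The sentence about a default to resuscitation stands in a sample-size paragraph and speaks of no decision, not of no ReSPECT form. The shares there (70% plus 20-30%) leave up to 10% unallocated. The harm model in 5.5 names only two care groups and leaves out No Decision, so patients without a form might drop out of it. The nested DNACPR models use the recommendation on the ReSPECT form as a covariate, with the same possible effect. Section 5.3 is a summary list, and the case report form and its completion guide are not shown.

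This stands in part. A reader might infer that the protocol prescribes the miscoding; it does not. But dropping these patients conflicts with the 200 harms (Step 1), and nothing in WP3 says how a DNACPR order on another form is recorded, separated or excluded.

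Three further inferences go beyond the documents:

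- **Old hospital forms carry over at these sites.** The 80% use of the national DNACPR form in 4.3 is a 2014 figure for all Acute Trusts. The earlier systems at the six sites are not stated, and 2.2 wants ReSPECT in place before data collection. Only patients bringing other forms in from outside rest on the text.
- **The estimate could be pulled below the null.** None of the cases computed does this; the lowest reading of a true 1.5 is 1.26.
- **The 22-30% share measures the bias.** That is the share of DNACPR holders missed. The bias in the harm contrast depends on the 1.2-7.0% of the comparator. Planned adjustment for comorbidity may also remove some of the difference due to frailty.

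**Conclusion.** The concern holds as a conditional one. The data listed for WP3 cannot identify the comparator that its aim defines, and the protocol itself expects the patients who would be misplaced. If patients without a form enter the DNACPR models, and 5-20% of the no-decision group hold a DNACPR on another form (an assumption), 30-180 patients are misclassified.

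The bias in the harm odds ratio is modest: a true 1.5 reads about 1.49 to 1.45 if hidden holders have the same risk as ReSPECT DNACPR patients, and 1.47 to 1.33 if their odds ratio is 3. These are crude figures, before adjustment. The models of DNACPR assignment are affected more directly, since 7-30% of holders would be recorded as not having one. This deserves correction in an exploratory work package but does not undermine it.

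**What to change.** - **Check the case report form first.** If it already records a DNACPR order on any form, only the 5.5 wording below is needed.
- **5.3, for sites not yet collected:** add one item recording whether any DNACPR order was in force on the assessment day, and its source (ReSPECT, other hospital form, community form).
- **5.5:** state that No Decision and no-DNACPR status require no order on any form. Keep patients with a non-ReSPECT DNACPR in a separate category outside the comparator. Say whether patients without a form enter the harm model, and reconcile this with the 200 harms.
- **Sites already complete** (the timetable in 7.5 shows five of six): add a sensitivity analysis of the DNACPR contrast restricted to patients with a ReSPECT form, and state the limitation. Patients with and without a form may differ in other ways, so a shift between the two analyses should not be read as misclassification alone.
- **Re-check notes only where the link list survives.** Section 5.4 allows its destruction under local procedures before data lock.

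The cost is one data item and a smaller comparator in the restricted analysis (1680 instead of 2580, about 4% on the standard error). Re-checking notes of patients without a form is real work, so it is optional. Clinical care is not affected.

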5.5 Data Analysis for WP3

Descriptive statistics will be used to summarise patient characteristics and outcomes according to patient personal preference, ReSPECT clinical treatment recommendation and resuscitation status. We will use appropriate multiple regression techniques to explore the associations between patient characteristics, resuscitation status (DNACPR or for resuscitation), care group and risk of harm and death. Firstly, by fitting a series of nested models with DNACPR (yes/no) as the dependent variable and patient characteristics and clinical treatment recommendation as indicated on the ReSPECT form) as the independent variables we will assess the influence of patient characteristics at baseline and patient preference on DNACPR decision and establish whether the patient preference adds information beyond that provided by the patient characteristics as regards the DNACPR decision. Secondly, we will use ordered logistic regression with care group ('Focus on Life-Sustaining Treatment' and 'Focus on Symptom Control' and 'No Decision') as the dependent variable and patient characteristics as the independent variables to assess whether patient characteristics influence the choice of care group. Finally, we will use logistic regression (conditional should we be able to match cases to controls), with and without adjustment for patient characteristics, with harm (yes/no, obtained from the NHS Safety Thermometer) as the dependent variable and care group ('Focus on LifeSustaining Treatment' and 'Focus on Symptom Control') and DNACPR (yes/no) as independent variables to assess whether focus of care group or DNACPR order independently influence risk of harm.

Sample size: As this is an exploratory analysis a formal sample size calculation is not appropriate.

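### As written, the WP3 harm model omits the 'No Decision' level, so its event count (195, stated as 200) and its DNACPR comparator do not match those in 5.5 and 5.1.1

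*Protocol*

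**What the plan says.** Protocol 5.5 (Data Analysis for WP3) describes three sets of regressions. The second is an ordered logistic model with "care group ('Focus on Life-Sustaining Treatment' and 'Focus on Symptom Control' and 'No Decision') as the dependent variable", so care group there has three levels. The third is the harm model, a logistic regression fitted with and without patient characteristics. It has harm as the outcome and "care group ('Focus on LifeSustaining Treatment' and 'Focus on Symptom Control') and DNACPR (yes/no) as independent variables". Here care group has two named levels, and the text does not say how patients without a decision are coded.

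The sample-size text in 5.5 plans 3000 patients over six sites and assumes a harm rate of 6.5%, concluding that "this will provide 200 incidences of harm for the risk modelling". It also says "we expect 70% of patients to have a ReSPECT decision, of whom 20% will have a DNACPR decision" and "20-30% will have no decision, which by default means they would receive resuscitation in the event of cardiac arrest".

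Section 5.1.1 sets the question: whether DNACPR recommendations made within ReSPECT "increase the risk of certain harms when compared with not having a DNACPR order in place". Section 5.1.3, question 5, asks whether DNACPR independently predicts harm.

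**The concern.** The two care-group levels in the harm model are boxes on the ReSPECT form (Appendix 1). A patient with no form has neither. If the model is run as listed, standard software drops patients with a missing covariate, and the analysis set shrinks to those with a ReSPECT decision.

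Two things in the protocol would then no longer fit. The harms available to the model would be fewer than the number put forward for it. And DNACPR patients would be compared with patients who have a form and are for CPR, whereas the aim in 5.1.1 compares them with everyone who has no DNACPR order, including those with no decision at all. Section 5.3.1 says an excess of harms arising from DNACPR orders will lead to the conclusion that more work is needed to prevent them. The reader of that conclusion needs to know who the comparison group was.

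**Working it through.** **Inputs, all from protocol 5.5.** N = 3000; harm rate 6.5%; 70% with a ReSPECT decision; 20% of those with DNACPR; 20-30% with no decision. The protocol gives no harm rate by group, so an equal 6.5% in each group is my assumption unless stated.

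**1. The plan's own figure.** 3000 x 0.065 = 195, which rounds to the stated 200. It reproduces only with all 3000 patients in the model.

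**2. The harm model read literally (no-decision patients have no care-group value).**

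| No decision | Patients left | Harms left | Below 195 |
|---|---|---|---|
| 20% | 3000 x 0.80 = 2400 | 2400 x 0.065 = 156 | 39 |
| 30% | 3000 x 0.70 = 2100 | 2100 x 0.065 = 136.5 | 58.5 |

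The 30% row is the one that agrees with 70% having a decision.

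**3. Sensitivity to the equal-rate assumption.** Hold the overall total at 195 and let the rate in no-decision patients be 3% or 8% (assumed).
- At 3%: 195 - 600 x 0.03 = 177, or 195 - 900 x 0.03 = 168.
- At 8%: 195 - 600 x 0.08 = 147, or 195 - 900 x 0.08 = 123.

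**4. The DNACPR contrast.** DNACPR patients: 3000 x 0.70 x 0.20 = 420, with 420 x 0.065 = 27.3 harms.
- Comparator in 5.1.1: 3000 - 420 = 2580 patients, 167.7 harms.
- Comparator among form-holders only: 2100 - 420 = 1680 patients, 109.2 harms.

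**5. Effect on precision.** The approximate variance of an unadjusted log odds ratio is the sum of the reciprocals of the four cell counts.
- All patients: 1/27.3 + 1/392.7 + 1/167.7 + 1/2412.3 = 0.0456, standard error 0.213.
- Form-holders: 1/27.3 + 1/392.7 + 1/109.2 + 1/1570.8 = 0.0490, standard error 0.221.

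The standard error rises by about 4%. The 27 harms in the DNACPR group dominate the variance, and they are the same in both cases. The further effect of adjusting for care group cannot be computed, because the protocol does not give the joint distribution of care group and DNACPR.

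**6. Does keeping 'No Decision' restore the comparator?** Take the ordinary (unmatched) logistic model without patient characteristics and with 'No Decision' as reference:

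logit(risk) = a + c1 x (life-sustaining) + c2 x (symptom control) + b x DNACPR

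- No-decision patients: all have DNACPR = no, so logit(risk) = a. They determine a and nothing else.
- Form-holders: the intercepts are a + c1 and a + c2. As c1 and c2 are free, these intercepts are not constrained by a.

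So b is fitted from form-holders alone and is the same whether no-decision patients are kept or dropped. With patient characteristics in the model, no-decision patients affect b only indirectly, through the covariate coefficients. In either case b compares DNACPR with no DNACPR among form-holders in the same care group, which is not the comparison in 5.1.1.

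**The case against.** The strongest reply is that nothing in the protocol excludes patients without a decision. The two named terms could be indicators with 'No Decision' as the unnamed reference, which keeps 3000 patients and 195 harms. Other text points that way: 5.1.4 records the absence of a ReSPECT decision as data, 5.5 treats such patients as for resuscitation by default (so they do have a DNACPR value), and the harms are counted over everyone. This stands as far as it goes, so dropping them is a literal reading and not a stated rule. It does not rescue the comparator, as step 6 shows.

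A second reply is that care group and DNACPR are entered together on purpose, to see whether each independently influences harm, and that the analysis is declared exploratory. Both are true. The joint model is a legitimate second question, and the exploratory label excuses the absence of a formal sample-size calculation. Neither supplies a model for the comparison that 5.1.1 names.

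A reader might infer more than the text supports:
- **That 200 is an arithmetic error.** It is a fair rounding of 195; the issue is which patients it counts.
- **That the event count is the sole basis for 3000 patients.** Section 5.5 also gives generalisability and a spread of decisions as reasons.
- **That care group and DNACPR nearly coincide.** No figure shows this, and the form records them as separate items.
- **That uptake will be well below 70%.** Section 3.2.4 does mention infrequent completion, but only on take and on post-take rounds, when scheduling WP1a observation. It says nothing about the share of in-patients with a form in WP3.

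**Conclusion.** The concern holds as an internal inconsistency. The harm model lists two care-group levels where the preceding model lists three. On the literal reading it would contain 2100-2400 patients and about 137-156 harms instead of 195, assuming an equal 6.5% rate. If the rate in no-decision patients lay between 3% and 8%, the range would be 123-177.

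The more important part does not depend on that reading. With care group in the model, the DNACPR term without covariates rests on form-holders only, however 'No Decision' is coded, so the model described does not deliver the contrast in 5.1.1. The effect on precision is small. What changes is the question answered, together with a count of 200 that says little about the DNACPR contrast, where only about 27 harms are expected in the DNACPR group.

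**What to change.** Amend 5.5 as follows.

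1. Add a harm model with DNACPR (yes/no) and no care-group term, fitted with and without patient characteristics on all patients. Code patients without a decision as no DNACPR, in line with the default already described in 5.5. This is the model that answers 5.1.1.
2. In the model that adds care group, use three levels including 'No Decision'. State that its DNACPR term compares patients who have a ReSPECT decision, within care group.
3. Restate the event count: about 195 harms expected overall, of which about 27 in the roughly 420 DNACPR patients if the harm rate is equal across groups.

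The cost is one extra model, a few lines of text and a less favourable stated count for the DNACPR contrast. No extra patients or data items are needed, since 5.1.4 already collects the absence of a decision.

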5.1.4 Methods

We will conduct a retrospective case-note review that is synchronised with the routine collection of NHS Safety Thermometer data. In addition information on patient demographics, admission, comorbidities and functional status and ReSPECT decisions (or absence of ReSPECT decisions) will be extracted from clinical records. We will explore the associations between patient characteristics, resuscitation status, care group and risk of harm.

Assessments will be co-ordinated to occur simultaneously with the routinely collected NHS Thermometer Audit data. The majority of NHS Trusts contribute to the NHS Safety Thermometer programme. In the event that a research site does not routinely collect NHS Safety Thermometer data (or the national programme is unexpectedly withdrawn) they will be asked to collect Classic Safety Thermometer data for research purposes.

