5.3.1 Outcomes

As our measure of patient harm we will use the data collected for the NHS Safety Thermometer. In participating Acute Trusts this point of care survey collects data on 100% of inpatients for one day each month. Our outcome of interest in the Classic Thermometer is 'harm free care' defined as none of the defined adverse events being present on the day of the assessment (pressure ulcers, urine infections in catheterised patients, falls, or venous thromboembolism). These are all events that would be associated with less intense care. If as a consequence of a DNACPR order, there are more of these events we will conclude that more work is needed to prevent iatrogenic harms caused by DNACPR orders leading to a lower level of care.

A second harm measure, the 'Medication Thermometer', is being rolled out in the NHS. This also a point of care survey collecting data on 100% of in-patients for one day each month. Our outcome of interest here is 'drug induced harm'. The survey identifies people who are using a specified list of high-risk medicines. There is then a discussion between a nurse, doctor and a pharmacist to assess if the patient has been harmed and the level of any harm. Harm will be defined as a moderate (or greater) incident which results in a moderate increase in treatment and which caused significant but not permanent harm. We will collect Medication Thermometer data where it is routinely available.

Standardisation of Data collection: NHS Safety Thermometer data will be extracted by NHS audit, clinical or site research staff who have been trained in the use of the tool. We are aware of variation in Thermometer measurements and will develop a training set of standardised cases in to improve consistency. We will work closely with the six sites to ensure the approach is standardised and report on reliability from the standardised cases.

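### WP3 gives greater power as its reason for matching cases to controls, but the whole cohort is already collected, so matching cannot add power and a fixed ratio loses some

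*Protocol*

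**What the plan says.** Protocol section 5.5 sets the WP3 size: "We therefore intend to enrol 3000 patients in this study (minimum 500 patients per site, six sites". It assumes a harm rate of 6.5% and expects 200 harms for the risk modelling. On exposure it says "we expect 70% of patients to have a ReSPECT decision, of whom 20% will have a DNACPR decision".

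The final model in section 5.5 has harm (yes/no) as the outcome, and care group and DNACPR (yes/no) as the explanatory variables. The method is "logistic regression (conditional should we be able to match cases to controls), with and without adjustment for patient characteristics". The sample-size text closes with the reason for matching: "If possible, for the modelling of harms, we will match cases to controls in order to increase statistical power". No other reason is given, and no ratio, matching variables or outside source of controls is named.

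Section 5.3.1 says of the harm measure that "this point of care survey collects data on 100% of inpatients for one day each month". Section 5.1.4 has demographics, comorbidities, functional status and ReSPECT decisions taken from the notes, and covers patients who have no such decision ("or absence of ReSPECT decisions) will be extracted from clinical records").

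**The concern.** Matching is efficient when data on controls still have to be gathered: it makes a limited number of controls more informative. WP3 is not in that position. The number of cases is fixed by the harm rate, and exposure, covariates and outcome are recorded for every non-case too. Selecting matched controls from that set can only leave out information already paid for, so the stated reason does not fit the design.

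The estimate affected is the answer to research question 5 in section 5.1.3, whether DNACPR independently predicts harm. Section 5.3.1 ties a conclusion about practice to that answer. Few exposed harms are expected (about 27 under no association), so needless imprecision makes it easier to miss a real excess of harm.

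**Working it through.** **Inputs from protocol section 5.5:** 3000 patients; 6.5% harm; 70% with a ReSPECT decision, of whom 20% have DNACPR. **Assumed, because the protocol gives none:** two-sided alpha 0.05, 80% power, the odds ratios (OR) examined and the matching ratios (m controls per case).

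**1. The plan's own figure.** 3000 × 0.065 = 195 harms, against 200 stated. The difference is rounding, and the figure is reproduced. Non-cases: 3000 − 195 = 2805, or 2805/195 = 14.4 per case already in the data.

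**2. Exposure.** 0.70 × 0.20 = 0.14, so about 420 of 3000 patients have DNACPR. Under no association the four cells are 27.3 and 167.7 (cases with and without DNACPR) and 392.7 and 2412.3 (non-cases with and without DNACPR).

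**3. Standard error (SE) of the log OR under no association**, as the square root of the summed reciprocals of the cells:
- Everyone: √(1/27.3 + 1/167.7 + 1/392.7 + 1/2412.3) = 0.213.
- 1:1: √(2 × (1/27.3 + 1/167.7)) = 0.292, which is 37% larger. Uses 390 patients and drops 2610 non-cases.
- 1:4: 0.231, which is 8% larger. Uses 975 and drops 2025.
- 1:10: 0.216, which is 1% larger. Uses 2145 and drops 855.

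**4. Detectable OR.** Let p0 = 0.14 be exposure in non-cases and p1 = OR × p0/(1 − p0 + OR × p0) exposure in cases. Then SE² = 1/(195 × p1 × (1 − p1)) + 1/(195 × m × p0 × (1 − p0)). Solve log(OR) = (1.96 + 0.84) × SE:
- Everyone (m = 14.4): OR 1.67 (p1 = 0.214, SE = 0.183).
- 1:1: OR 2.09 (p1 = 0.254, SE = 0.264).
- 1:4: OR 1.76 (p1 = 0.222, SE = 0.201).

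A two-proportion formula gives 1.70, 2.07 and 1.78. The shortcut exp(2.80 × SE) with the SE from step 3 should not be used: it gives 1.82, 2.27 and 1.91, which are too high because exposure among cases rises under the alternative.

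**5. Power at fixed odds ratios** (two-proportion formula), for OR 1.5 / 1.75 / 2.0:
- Everyone: 57% / 84% / 96%.
- 1:1: 32% / 56% / 76%.
- 1:4: 50% / 78% / 93%.

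**6. Check with confounding.** Steps 3 to 5 are unadjusted. A simulation of 3000-patient cohorts (300 runs per scenario, OR 1.75) compared adjusted logistic regression on everyone with conditional regression on matched sets. Mean SE for full cohort, 1:1 and 1:4:
- No confounding: 0.185, 0.280, 0.206.
- Moderate: 0.181, 0.270, 0.198.
- Strong: 0.176, 0.249, 0.188.

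Power ranged over 80–87% (full cohort), 52–64% (1:1) and 75–83% (1:4). Matching did not exceed the adjusted full cohort in any scenario.

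**The case against.** The strongest reply has four parts.

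- **Matching is optional.** Section 5.5 calls the analysis exploratory, declines a formal sample-size calculation and promises no power. Both mentions of matching carry a condition, as in "logistic regression (conditional should we be able to match cases to controls", and the default is ordinary logistic regression. All this stands and lowers the weight of the point. A reader might infer that a stated power claim fails or that the 3000 target is undermined; the document supports neither, since neither the target nor the 200 harms depends on matching.
- **No ratio is given.** A reader might infer 1:1 matching and a 37% loss. The text does not say so. At 1:10 the loss is about 1%, and variable-ratio or stratified matching could keep nearly everyone. This stands as to size. It does not rescue the rationale: a scheme that keeps everyone has no meaningful advantage over covariate adjustment.
- **Matching deals with confounding**, which matters because DNACPR patients are likely to be sicker. That is a legitimate aim, but it is not the one stated, and the planned adjustment addresses the same measured characteristics without dropping anyone.
- **Details can wait for an analysis plan.** Ratio and matching variables can, and their absence is no fault here. A later plan cannot make the stated reason true.

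Three other readings also go too far. A reader might infer that the decision to match would follow inspection of the results, but no timing is given. The text says without adjustment; it does not promise a crude estimate that matching would take away. And matching is described for harm cases, so losses computed for matching DNACPR patients to others answer a design the protocol does not describe.

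**Conclusion.** The point holds as a wrong rationale for an optional analysis. With data on about 195 cases and 2805 non-cases in hand, matching cannot raise power over adjusted regression on the full cohort, and any fixed ratio below the available 14.4 per case lowers it. How much it lowers it depends on the unstated ratio, from slight at 1:10 to severe at 1:1.

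The figures rest on the protocol's 6.5% harm and 14% DNACPR, an assumed two-sided 0.05 and 80% power, no adjustment and no allowance for clustering by hospital. The simulation gives the same direction under the three confounding strengths tried, which are themselves assumptions. Because the analysis is exploratory and the default model is already suitable, the issue is moderate and not one that must be fixed before the study can proceed.

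**What to change.** In section 5.5, delete the claim that matching increases power. State that the main harm model is unconditional logistic regression on all enrolled patients, reported with and without adjustment for patient characteristics. If matching is kept, label it a sensitivity analysis for confounding, with its ratio and matching variables set in advance. The cost is a change of wording: no further data are needed, and dropping matching altogether would save work.
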